11.3 Vital Signs

The following vital signs measurements will be taken at the time points specified in the Schedule of Events (refer to the Protocol):

- 1 Pulse Rate (beats/min);
- 2 Systolic blood pressure (SBP) (mmHg)
- 3 Diastolic blood pressure (DBP) (mmHg)
- 4 Respiratory rate (breaths/min)
- 5 Body temperature (°C)

All vital signs data collected at scheduled and unscheduled visits will be included in the listings, but only results collected as scheduled visits will be included in the summary tables.

The parameter names that will be used in the outputs will comprise of the test name and the unit of measure, for example, 'Systolic Blood Pressure (mmHg)'. Parameters will be sorted in the order that the measurements were collected in on the Vital Signs eCRF page within the tables and listings.

Vital signs measurements will present summary statistics for the results at the baseline and each scheduled post-baseline visit for each of the parameters. In addition, summaries will be presented for the change from baseline values at each scheduled post-baseline visit (continuous descriptive analysis).

The decimal precision to which the summaries for each parameter will be presented will be based on the maximum number of decimals to which the results were reported on the eCRF.

11.4 12-Lead Electrocardiogram (ECG)

The following ECG measurements will be taken at the time points specified in the Schedule of Events (refer to the Protocol):

- 1 Heart Rate (bpm)
- 2 PR Interval (msec)
- 3 QT Interval (msec)
- 4 QTcF Interval (msec)
- 5 QRS Duration (msec)
- 6 ECG clinical interpretation

All ECG data collected at scheduled and unscheduled visits will be included in the listings, but only results collected as scheduled visits will be included in the summary tables.

The parameter names that will be used in the outputs will comprise of the test name and the unit of measure, for example, 'Ventricular Rate (beats/min)'. Parameters will be sorted in the order that the measurements were collected in on the ECG eCRF page within the tables and listings.

ECG measurements will present summary statistics for the results at the baseline and each scheduled post-baseline visit for each of the parameters. In addition, summaries will be presented for the change from baseline values at each scheduled post-baseline visit (continuous descriptive analysis).

The decimal precision for each parameter will be based on the maximum number of decimals to which the results were reported on the eCRF.

The summary of overall interpretation findings table will present counts and percentages for the reported results at baseline and each post-baseline visit/time point. Result categories will be ordered as 'Normal', 'Abnormal Not Clinically Significant (NCS)' and 'Abnormal Clinically Significant (CS)' (categorical descriptive analysis).

11.5 Physical Examinations

Complete physical examinations will be performed by a licensed physician at the time points specified in the study schedules.

A complete physical examination will include, at a minimum, assessments of the cardiovascular, respiratory, gastrointestinal, and neurological systems.

By-subject data listings will be presented at the time points collected for complete physical examination parameters and Symptom directed physical examination parameters.

11.6 Pregnancy and Follicle Stimulating Hormone (FSH) Tests

All information related to pregnancy testing (urine and serum based) and contraception status will be presented in the by-participant data listings. Follicle stimulating hormone (FSH) test for postmenopausal women will be presented in the data listing.

12. IMMUNOGENICITY

Not Applicable for this study.

13. CHANGES TO THE PLANNED ANALYSIS

Not applicable.

14. INTERIM AND FINAL ANALYSIS**14.1 Interim Analysis**

No Interim analysis planned for this study.

14.2 Final Analysis (End of Study)

The final analysis will be conducted after all participants have completed the study, the clinical database has been locked, the analysis populations have been approved and the study has been unblinded.

The final analysis will be based on the final version of SAP. Any deviations from the planned analysis will be documented in the CSR.

15. SOFTWARE

- SAS[®] Version 9.2 or higher (SAS Institute, Cary, North Carolina, USA).

16. APPEENDIX

16.1 Appendix 1: Schedule of Assessments (Stage 1)

Assessment	Screening	Treatment	Follow-up		
	Screening	Day 1*	Week 1	Week 2	Week 4
Day	-28 to -1	1	8 ± 4 days	15 ± 4 days	29 ± 4 days
Visit	1	2	3	4/ ET	5 /EOS
Informed Consent	X				
Inclusion/Exclusion	X	X			
Demographics	X				
Medical History and Prior Medications ¹	X				
Subject Diary ²		X	X	X	X
Anthropometric Parameter ³	X	X	X ¹⁸	X	X
Abdominal or Thigh Ultrasound ⁴	X	X		X ¹⁷	X
Medical Examinations					
Physical Examination ⁵	X	X	X ¹⁶	X ¹⁶	
Injection site assessments ⁶		X	X	X	X
Vital Signs ⁷	X	X	X ¹⁶	X ¹⁶	
ECG ⁸	X	X	X ¹⁶	X ¹⁶	
Laboratory Evaluation					
Blood Tests ⁹	X	X	X ¹⁶	X ¹⁶	
Urinalysis ¹⁰	X	X	X ¹⁶	X ¹⁶	
Pregnancy Status ¹¹	X	X		X ¹⁶	
Virology ¹²	X				
IP Administration		X			
Photography ¹³		X	X	X	X
AE ¹⁴		X	X	X	X
Concomitant Medication		X	X	X	X ¹⁵

AE: Adverse event; AESI: Adverse event of special interest; Ag/Ab: Antigen/antibody; ALP/ALKP: Alkaline phosphatase; ALT: Alanine aminotransferase; aPTT: Activated partial thromboplastin time; AST: aspartate aminotransferase; β-hCG: Beta human chorionic gonadotropin; ECG: Electrocardiogram; eGFR: Estimated glomerular filtration rate; EOT: End of treatment; EOS: End of study; ET: Early Termination; FBS: Fasting blood sugar; GGT: Gamma-glutamyl transferase; Hb: Hemoglobin; HbA1c: Hemoglobin A1c; HBV:

Hepatitis B Virus; Hct: Hematocrit; HCV: Hepatitis C Virus; HDL-C: High-density lipoprotein cholesterol; HIV: Human immunodeficiency virus; INR: International normalized ratio; IP: Investigational product; ISR: Injection site reaction; LDL-C: Low-density lipoprotein cholesterol; RBC: Red blood cell; SAE: Serious adverse event; TBIL: Total bilirubin; WBC: White blood cell; WOCBP: Woman of childbearing potential.

- * Available measurements of clinical evaluations (physical examinations, vital signs, and ECG) and laboratory evaluations (biochemistry, hematology, coagulation, and urinalysis) within 14 days prior to IP dose can be accepted as the Baseline value and will not necessitate duplicate examinations.
 - * If study drug dose is within 7 days of Screening pregnancy test, pregnancy test at Visit 2 (Day 1) will not be necessary to assess.
 - * In cases where more than 1 data is available for a certain evaluation, the latest value prior to the study drug administration will be used as the Baseline value.
- ¹ Details of concurrent medical conditions, prior surgical procedures, and chronic diseases or other significant medical events prior to Screening will be collected. Any other non-significant medical events within 6 months prior to Screening will also be collected. Prior medications include a complete history of previous treatment/medications within 6 months prior to Screening.
 - ² Subject diaries will be provided to the subjects on Day 1. The subjects will be asked to record if there are any changes to the injection site/s or any discomforts from Day 1 until last clinic visit or when all ISRs have resolved or stabilized. The diary will be reviewed at the following visits as needed.
 - ³ Anthropometric parameters to be collected include body height and body weight. Body height will be measured at Screening only. Thigh circumference will be collected only for Group 1 (320 mg) in Stage 1 study.
 - ⁴ Ultrasound – Thickness of fat will be obtained by ultrasonic measurements across target area. Abdominal or thigh ultrasound will be performed at Screening, Day 1, and Week 4. Abdominal or thigh ultrasound may be performed within 4 days before Day 1 and up to 4 days before/after Week 4 follow-up visit. Day 1 ultrasound can be exempted if the screening ultrasound is performed within 4 days prior to IP dose, and the screening ultrasound can be accepted as the Baseline value.
 - ⁵ A complete physical examination will include, at a minimum, assessments of the cardiovascular, respiratory, gastrointestinal, and neurological systems.
 - ⁶ On Day 1, injection site assessments will be performed pre-dose and at 1-hour post-dose.
 - ⁷ On Day 1, vital signs assessments to be performed pre-dose and at 1-hour post-dose. Vital sign assessments include temperature, pulse rate, blood pressure, and respiratory rate. At simultaneously scheduled assessments, vital signs will be collected prior to any blood draws.
 - ⁸ On Day 1, ECG assessments will be performed pre-dose only. ECG to be performed in supine position after at least 5 minutes rest. The following ECG parameters will be recorded: heart rate, RR interval, PR interval, QT interval, QTc interval, and QRS interval.
 - ⁹ Blood tests include biochemistry, hematology, and coagulation assessments. Biochemistry assessments include albumin, ALT, AST, ALP, triglyceride, total cholesterol, LDL-C, HDL-C, TBIL, GGT, urea, creatinine, eGFR, HbA1c, FBS, Sodium, Potassium, Bicarbonate, and Chloride. Hematological assessments include Hb, Hct, RBC count, mean corpuscular volume, Leukocyte/white blood cell (WBC) count, WBC differential, and platelet count. Coagulation assessments include aPTT, Prothrombin time, and INR.
 - ¹⁰ Urinary samples for dipstick will be collected. On Day 1, collection will be performed pre-dose only.

- ¹¹ Serum β -hCG test will be taken for WOCBP at Screening visit only. FSH test is required for females who are post-menopausal at the Screening visit. Urine β -hCG strip test will be taken WOCBP for other scheduled visits.
- ¹² Virology tests include HIV/HBV/HCV infection test. Active HIV infection is detected by detectable positive HIV Ag/Ab combo test; active HBV: HBsAg; active HCV: positive anti-HCV antibody.
- ¹³ On Day 1, photography will be performed pre-dose and at 1 hour post-dose on Day 1. Other timepoints on Day 1 can be added to record the ISR at the discretion of the Investigator.
- ¹⁴ The occurring AEs/SAEs (including AESI) will be followed until resolution or the event is considered stable.
- ¹⁵ Collected only if a medication is related to AEs following the visit 4.
- ¹⁶ Assessment/collection can be performed on or within 4-days window prior to visit date.
- ¹⁷ Abdominal or thigh ultrasound only applicable to ET visit and not required for Week 2 visit.
- ¹⁸ At Week 1, only body weight will be measured and collected for anthropometric parameter.

16.2 Appendix 2: Schedule of Assessments (Stage 2)

Assessment/Schedule	Screening	Treatment				Follow-up	
		1	2	3	4	5/EOT	**6/ET
Visit	1	2	3	4	5/EOT	**6/ET	7/EOS
Day	-28 to -1	1*	(Visit 2 + 4 weeks)	(Visit 3 + 4 weeks)	(Visit 4 + 4 weeks)	(Visit 5 + 4 weeks)	(Visit 5 + 8 weeks)
Visit window		-	+ 7days	+ 7days	+ 7days	± 7days	± 7days
Informed Consent	X						
Inclusion/Exclusion	X	X					
Demographics	X						
Medical History and Prior Medications ¹	X						
Subject Diary		X	X	X	X	X ¹⁴	X ¹⁴
Anthropometric Parameter ²	X	X	X	X	X	X	X
Efficacy Assessment							
Abdominal Ultrasound ³		X	X	X	X	X	X
9-Point CBL-514 Satisfaction Questionnaire						X	
Medical Examinations							
Physical Examination ⁴	X	X ¹⁶	X ¹⁶	X ¹⁶	X ¹⁶	X ¹⁶	X ¹⁶
Injection site assessments ⁵		X	X	X	X	X	X
Vital Signs ⁶	X	X ¹⁶	X ¹⁶	X ¹⁶	X ¹⁶	X ¹⁶	
ECG ⁷	X	X ¹⁶				X ¹⁸	
Laboratory Evaluations							
Blood Tests ⁸	X	X ¹⁶	X ¹⁶	X ¹⁶	X ¹⁶	X ¹⁶	
Urinalysis ⁹	X	X ¹⁶	X ¹⁶	X ¹⁶	X ¹⁶	X ¹⁶	
Pregnancy Status ¹⁰	X	X ¹⁶	X ¹⁶	X ¹⁶	X ¹⁶	X ¹⁶	
Virology ¹¹	X						
Photography ¹²		X	X	X	X	X	X
Randomization		X					
CBL-514 or Placebo Administration ¹⁷		X	X	X	X		
Adverse Events ¹³		X	X	X	X	X	X

Assessment/Schedule	Screening	Treatment				Follow-up	
		2	3	4	5/EOT	**6/ET	7/EOS
Visit	1	2	3	4	5/EOT	**6/ET	7/EOS
Day	-28 to -1	1*	(Visit 2 + 4 weeks)	(Visit 3 + 4 weeks)	(Visit 4 + 4 weeks)	(Visit 5 + 4 weeks)	(Visit 5 + 8 weeks)
Visit window		-	+ 7days	+ 7days	+ 7days	± 7days	± 7days
Concomitant Medication		X	X	X	X	X	X ¹⁵

AE: Adverse event; AESI: Adverse event of special interest; Ag/Ab: Antigen/antibody; ALP/ALKP: Alkaline phosphatase; ALT: Alanine aminotransferase; aPTT: Activated partial thromboplastin time; AST: aspartate aminotransferase; β -hCG: Beta human chorionic gonadotropin; BMI: Body mass index; ECG: Electrocardiogram; eGFR: Estimated glomerular filtration rate; EOT: End of treatment; EOS: End of study; ET: Early Termination; FBS: Fasting blood sugar; FSH: Follicle stimulating hormone; GGT: Gamma-glutamyl transferase; Hb: Hemoglobin; HbA1c: Hemoglobin A1c; HBV: Hepatitis B Virus; Hct: Hematocrit; HCV: Hepatitis C Virus; HDL-C: High-density lipoprotein cholesterol; HIV: Human immunodeficiency virus; INR: International normalized ratio; ISR: Injection site reaction; LDL-C: Low-density lipoprotein cholesterol; RBC: Red blood cell; SAE: Serious adverse event; TBIL: Total bilirubin; WBC: White blood cell; WOCBP: Woman of childbearing potential.

* Available measurements of clinical evaluations (physical examinations, vital signs, and ECG) and laboratory evaluations (biochemistry, hematology, coagulation, and urinalysis) within 14 days prior to CBL-514 or Placebo dose can be accepted as the Baseline value and will not necessitate duplicate examinations.

* If study drug dose is within 7 days of Screening pregnancy test, pregnancy test at Visit 2 (Day 1) will not be necessary to assess.

* In cases where more than 1 data is available for a certain evaluation, the latest value prior to the study drug administration will be used as the Baseline value.

** The first follow up visit (Visit 6) should be performed 4 weeks post the final treatment. If treatment is cancelled at Visits 3, 4 or 5 due to the insufficient abdominal fat, it is recommended that first follow up visit is performed on the same day of the treatment cancellation. If not, then +7 days visit window should be utilized to schedule another day to complete the first follow up visit.

¹ Details of concurrent medical conditions, prior surgical procedures and chronic diseases or other significant medical events prior to Screening will be collected. Any other non-significant medical events within 6 months prior to Screening will also be collected. Prior medications include a complete history of previous treatment/medications within 6 months prior to Screening.

² Anthropometric parameters include body height, body weight and abdominal skinfold thickness measured by caliper. Body weight will be measured at all visits to calculate the BMI. Body height and abdominal skinfold thickness (by caliper) will be measured at Screening only.

³ Ultrasound – Thickness of fat will be obtained by ultrasonic measurements across target area. Abdominal ultrasound will be performed within 4 days before Visit 2 (Day 1), Visits 3, 4 and 5; and 4 days before/after the follow-up visits.

- 4 A complete physical examination will include, at a minimum, assessments of the cardiovascular, respiratory, gastrointestinal, and neurological systems and will be performed pre-dose.
- 5 On Visit 2 (Day 1), Visit 3, Visit 4, and Visit 5, the injection site assessments will be performed pre-dose and post-dose. Subjects will document any change to the ISRs in between visits in the Subject Diaries.
- 6 On Visit 2 (Day 1), Visit 3, Visit 4, and Visit 5, vital signs assessments to be performed pre-dose. Vital sign assessments include temperature, pulse rate, blood pressure, and respiratory rate.
- 7 On Visit 2 (Day 1), ECG assessments will be performed pre-dose. ECG to be performed in supine position after at least 5 minutes rest. The following ECG parameters will be recorded: heart rate, RR interval, PR interval, QT interval, and QRS interval.
- 8 Blood tests include biochemistry, hematology, and coagulation assessments. Biochemistry assessments include albumin, ALT, AST, ALP, triglyceride, total cholesterol, LDL-C, HDL-C, TBIL, GGT, urea, creatinine, eGFR, HbA1c, FBS, Sodium, Potassium, Bicarbonate, and Chloride. Hematological assessments include Hb, Hct, RBC count, mean corpuscular volume, WBC count, WBC differential, and platelet count. Coagulation assessments include aPTT, Prothrombin time, and INR.
- 9 Urinary samples for dipstick will be collected.
- 10 Serum β -hCG test will be taken for WOCBP at Screening visit only. FSH test is required for females who are post-menopausal at Screening visit. Urine β -hCG strip test will be taken for WOCBP for other scheduled visits.
- 11 Virology tests include HIV/HBV/HCV infection test. Active HIV infection is detected by detectable positive HIV Ag/Ab combo test; HBV: HBsAg; HCV: positive anti-HCV antibody.
- 12 On Visit 2 (Day 1), Visit 3, Visit 4, and Visit 5, the photography will be performed pre-dose. The post-dose photography will be performed only when any severe or unusual ISR was observed and assessed by Investigator after IP administration.
- 13 The occurring AEs/SAEs (including AESI) will be followed until resolution or the event is considered stable.
- 14 On follow-up visits, no subject diary will be provided to subjects and only review and recording of subject diary entries will be conducted.
- 15 Collected only if a medication is related to AEs following the Visit 6
- 16 Assessment/collection can be performed on or within 4-days window prior to visit date.
- 17 Eligible subjects will be randomly assigned to either the CBL-514 group or placebo group at a ratio of 2:1.
- 18 ECG assessment can be performed on or within 4 days before or after Visit 6/ET

16.3 Appendix 3: MMRM Assumptions Testing

a) Sphericity assumption

The first assumption of the MMRM analysis is sphericity, posits that the repeated measures of a within-subjects effect should have equal variances and constant covariances.

- When the sphericity assumption is satisfied, the F-test in a standard analysis of variance is appropriate.
- When the sphericity assumption is violated, the F-test in a standard analysis of variance will be positively biased; that is, it will be more likely to make a Type I error (i.e., reject the null hypothesis when it is, in fact, true).
- Violation of sphericity was corrected using the Greenhouse–Geisser method.

b) Normality assumption

Kolmogorov-Smirnov normality test will be used to check normality of the data and the results will be presented.

SAS Proc to be used for normality testing:

```
ods output TestsForNormality = Normal;
proc univariate data=input normal plots;
var CFB; *CFB=Change from baseline;
histogram Diff /normal;
qqplot /normal (mu=est sigma=est);
run;
ods output close;
data Normality;
set Normal (where = (Test = 'Kolmogorov-smirnov'));
if pValue > 0.05 then Status = "Normal";
else Status = "Non-normal";
drop TestLab Stat pType pSign;
run;
```

Perform the following steps to check the normality of data.

1. First, check normality of data by pooling all visits data together if normality is achieved perform the parametric test.
2. If overall data doesn't show normality, check normality at each timepoint and if only few timepoints achieve normality, then still perform parametric test as normality can be assumed for non-normal timepoint.
3. If extreme outliers are present, then remove the outliers and check normality to perform parametric test.
4. Other normality tests result will be explored in case of departure from normality assumption.
5. If normality assumption is still violated, the normality will be assumed to perform parametric tests.

c) Test for Homoscedasticity

Homogeneity of variances between two treatment groups will be tested using Levene's test.

```
proc glm;  
class treat;  
model CHG = treat;  
means treat / hovtest=levene welch;  
  
run;
```

Note that only the results from the HOVTEST= and WELCH options in PROC GLM account for variance heterogeneity. All other results assume equal variances. If heteroscedasticity occurs, all the results will be adjusted for unequal variances by adding the DDFM=SATTERTHWAITTE option in the MODEL statement to adjust the degrees of freedom for the unequal variances.

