4.1 Population Descriptions

4.1.1 Intent-to-treat (ITT Population)

All assigned or randomized subjects, regardless of whether they receive treatment or not, will be included in the ITT population. Summaries, listings, and analyses by treatment group will be based on the subject's randomly assigned treatment, not what they actually received.

All demographic data analysis will be based on the ITT population. All listings will be presented by the ITT population.

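### SAP Appendix 16.3(b) step 3 allows undefined extreme outliers to be removed after the fact from the data for the Stage 2 ITT MMRM, with no benefit because the parametric model is run anyway

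*SAP*

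**What the plan says.** SAP Section 10 makes the Stage 2 MMRM for fat-volume change conditional on its assumptions, refers the checks to Appendix 16.3, and rules out any substitute method if they fail. Appendix 16.3(b) says: "Kolmogorov-Smirnov normality test will be used to check normality of the data and the results will be presented". The sample code analyses the raw change ("var CFB; *CFB=Change from baseline"), with no split by treatment, and labels the data normal when p exceeds 0.05. Five steps follow:

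1. The opening step pools visits: "First, check normality of data by pooling all visits data together if normality is achieved perform the parametric test".
2. Otherwise each visit is tested separately, and the parametric test goes ahead even where just a few visits pass, with normality taken as given for the rest.
3. The outlier step reads: "If extreme outliers are present, then remove the outliers and check normality to perform parametric test".
4. Further tests of normality may be tried.
5. The closing step settles the matter: "If normality assumption is still violated, the normality will be assumed to perform parametric tests".

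The SAP does not say what counts as extreme, whether a scan or a whole subject is removed, or whether the model is then fitted without the removed values. Section 17 lists no full-data sensitivity table. The MMRM results are reported for ITT and repeated for PP. Section 4.1.1 defines ITT broadly: "All assigned or randomized subjects, regardless of whether they receive treatment or not, will be included in the ITT population".

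**The concern.** The CBL-514 minus placebo difference at Visits 6 and 7 from this MMRM is the only between-arm efficacy estimate that Section 10 specifies. The responder table gives a separate exact interval for each arm and no difference. If valid scans are dropped because they are large, the estimate no longer describes the ITT data, and trimming the tails tends to make its interval too short. The responder table would still use those scans, so the two efficacy tables would rest on different data.

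Timing adds to this. Under Protocol 10.7 the sponsor, investigator and site staff know the allocation throughout Stage 2, and under SAP 14.2 the final analysis follows unblinding. A cut-off left undefined in the SAP would therefore be settled with arms and outcomes already visible.

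**Working it through.** **Figures from the documents.** The SAP attaches no number to the outlier step and gives no effect size or SD. The only usable figures are the arm sizes: 50 × (1 − 0.16) = 42 and 25 × (1 − 0.44) = 14, total 56. This reproduces Protocol Table S3 and SAP 2.5. Every other input below is an assumption.

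**Does any branch change the method?** A pass at step 1 leads to the parametric model. So does step 2 when only a few timepoints pass, step 3 after removal, and step 5 when normality still fails. Step 4 only adds tests. The model is the same throughout, so step 3 can change only which values enter it.

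**What is being tested?** At one visit with arms pooled, the variance is the residual variance plus p(1 − p)Δ². Assume p = 50/75 = 2/3, Δ = 200 mL and a residual SD of 60 mL in both arms. The residual part is 60² = 3,600 and the between-arm part is (2/3)(1/3)(200²) = 8,889. The share due to treatment is 8,889 / 12,489 = 71%. The check would mostly be looking at the drug effect, not at the residuals to which the MMRM assumption applies.

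**How often does the pooled test fail?** Simulations used five post-baseline visits, AR(1) correlation 0.75, and 50/25 or 42/14 subjects.
- Normal residuals, no effect: 7% to 12% (nominal 5%).
- Normal residuals, real effect: 21% to 91%, depending on effect and SDs.
- Skewed CBL-514 response: 98% to 100%.

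**Is step 3 then reached?** The SAP leaves this open. If step 3 applies only when no single visit passes, it was reached in 0% to 0.3% of trials with normal residuals and 1% to 17% with skewed response. A separate set of runs gave 0% to 8.5%. If its own condition (extreme values present) is the trigger, it can be reached whatever the tests show, and the failure rates above do not measure how often data would be removed.

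**Size once removal is applied.** Cut-offs are pooled over visits and arms. Figures are differences in mL, CBL-514 minus placebo.

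| Simulation (assumed inputs) | Rule | All data | After removal | Shrinkage |
|---|---|---|---|---|
| A: Visit 6, mean loss 190 vs 15, skewed, 50/25, 1,000 trials | 1.5 IQR | −175 | −139 | 36 |
| A | 3 SD | −175 | −157 | 18 |
| A | 3 IQR | −175 | −167 | 8 |
| B: Visit 7, worst case, skewed, 50/25, 600 trials | 1.5 IQR | −150.7 | −124.9 | 25.8 |
| B: all scenarios | 3 IQR | – | – | about 0 normal, 0 to 7 skewed |
| C: Visit 6, skewed, 50/25 and 42/14, 400 trials | 1.5 IQR | about −175 | −141 to −147 | 28 to 34 |
| C | 3 IQR | about −175 | −166 to −170 | 5 to 9 |

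With normal residuals, removal in C changed the estimate by at most about 3 mL. B used CBL-514 mean changes of −150 to −250 mL (SD 50 to 120), placebo mean 0 (SD 40 to 60) and within-subject correlation 0.7. B and C use a raw difference in means in place of the MMRM contrast. The MMRM borrows from a subject's retained visits, so its shift could differ.

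**Which arm loses values?** In B, the largest CBL-514 losses made up 70% to 100% of removed Visit 7 values with pooled-visit cut-offs, but 0% to 100% when cut-offs came from Visit 7 alone. One example of the reverse is 42/14, effect −200, SD 60 in both arms, normal data, 1.5 IQR at Visit 7: 98% of removed values were placebo. With the same settings but skewed response, about 8 values per trial were removed, 81% of them placebo, and the difference moved from −200.6 to −145.8 (54.8 mL).

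**The case against.** The strongest reply has five parts.

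- **The removal may serve only the check.** The list is introduced as a way of checking normality, and nothing states that the MMRM is fitted to reduced data. This is possible. But step 3 ends in performing the parametric test, and nothing limits removal to the check, so the wording needs correcting on either reading.
- **Step 2 may end the sequence first.** On that reading removal would be rare. This stands as a limit on frequency.
- **A 1.5-IQR fence marks mild outliers.** The word *extreme* suggests something nearer 3 IQR, where the shift is small. This stands, and the larger figures should not be quoted alone.
- **The analysis is secondary.** SAP Section 10 bars claims from its p-values and Protocol Section 16 plans no formal testing. This lowers the severity but does not repair a biased estimate or interval.
- **A discrepancy would be visible.** The by-visit summaries and the ultrasound listing do not apply the outlier step. This stands as partial mitigation.

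Two stronger readings are tempting. A reader might infer that values are deleted repeatedly until normality is reached. The text describes one removal and one re-check, and step 5 proceeds even if normality still fails. A reader might also infer that mainly the best CBL-514 responders would be lost. The documents do not say so. It follows from assumed skewness and cut-offs pooled over visits and arms, and other settings remove mostly placebo values. Pooling over arms is itself inferred from the sample code, since step 1 mentions visits only.

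**Conclusion.** The point holds as a should-fix. Step 3 permits a single, post hoc, undefined removal of observed values before the parametric analysis. It rests on a check of the wrong quantity, and steps 2 and 5 make it unnecessary. With cut-offs pooled over visits, the shrinkage is about 0 to 9 mL under 3 IQR, and up to about 26 to 36 mL under 1.5 IQR with skewed response (36/175 = 21% in the largest case). Cut-offs set on one visit can give more. In these simulations removal left the difference unchanged or moved it toward zero.

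The sizes rest on assumed effects, SDs, skewness and cut-offs, and they describe what happens once removal is applied, not how often it would be. The primary responder proportions do not use this appendix.

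**What to change.** Amend the SAP before the analysis is run:

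1. Delete step 3 of Appendix 16.3(b).
2. State in Section 10 that the MMRM is fitted to all observed values, in ITT and in PP.
3. Replace the remaining pass/fail steps with inspection of MMRM residuals by arm and visit, reported as a diagnostic that does not alter the model or the data.
4. Remove the Section 10 condition that the MMRM is used only if its assumptions are met, together with the sentence on alternatives that depends on it. Dropping step 5 without this would leave it unclear whether the model is run at all.
5. Allow outlier exclusion only as a sensitivity analysis beside the full-data result, with the cut-off, the unit removed (scan or subject) and the reference data fixed in advance.

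The cost is SAP wording and at most one optional sensitivity table. No new data are needed, and the primary analysis does not change.
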